CT abdomen/pelvis ^e	X											X ^f	X	X	X ^g
Bone scan ^e	X											X ^f	X	X	X ^g
Leukapheresis		X ^h	X		X		X						X ^{h,i}		
Sipuleucel-T infusion				X		X		X							
Tetanus immunization		X													
DNA immunization – ARM 2 PATIENTS ONLY ^a									X	X	X	X	X	X	
Blood for CTC analysis		X							X			X	X	X	X
Blood for immune studies ^j		X							X			X	X	X	X ^k

Note: Grey regions indicate those tests or procedures or visits only applicable to subjects treated on Arm 2. Acceptable delays in study treatments or procedures may result in corresponding delays of subsequent visits. Annual long term follow up will occur for up to five years. See Section 9 for more details.

^a ARM 2 Only: Biweekly DNA immunization (#1-3) can be +/- 3 days; quarterly DNA immunization (#4-6) can be +/- 7 days from expected date determined from prior visit.

^b Study coordinator or research nurse review of systems, including ECOG PS

^c CBC with differential and platelets to be performed within 72 hours prior to leukapheresis (for Sipuleucel-T treatment) unless an event occurs that would require it be drawn sooner for safety considerations, or if required sooner per institutional requirements or MD discretion. A CBC result within 7 days prior to leukapheresis for research is ideal.

^d PSA measurements must be performed at the 3-month intervals defined, but can be more frequent if clinically indicated.

^e Radiographic studies (CT scans and bone scans) can be performed +/- 7 days of the study visit

^f Staging studies (CT and bone scan): scan progression between Screening and Month 3 will not be used to define radiographic progression for the purposes of this study and will not necessitate subjects to come off study. Patients should come off study at this time point only due to symptomatic progression requiring other treatment for prostate cancer.

^g Radiographic studies not required at off-study time point if subject already met time-to-progression endpoint and/or studies already performed within 1 month; scans otherwise performed every 12 weeks

^h Leukapheresis collected (+/- 7 days) for research, not preparation of sipuleucel-T product

ⁱ If leukapheresis is not able to be obtained at Month 6 visit, then up to 150 ml may be obtained via peripheral blood draw as an alternative.

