Evidence that the toxicity rate is excessive will be considered sufficient if the lower limits of the 90% one-sided confidence intervals for the estimates of the true toxicity rates exceed the toxicity limits defined above (i.e., 20% for Grade 3 events and 10% for Grade 4 events), after the first 5 patients have been accrued. Operationally, this will occur if any of the following events occurs within a study arm: Grade ≥ 3 events (or Grade >1 autoimmune events) are present in at least 3 out of 5, 4 out of 9 (or less), 5 out of 13 (or less), or 6 out of 15 (or less) of the subjects accrued (within a study arm). Furthermore, accrual will be temporarily suspended if any of the following events occur: Grade 4 events are present in at least 2 out of 5, 3 out of 11 (or less), or 4 out of 15 (or less) of the subjects accrued (within a study arm).

If one of these thresholds is reached, accrual will be temporarily suspended and the study will be reviewed by the UW DSMC (data and safety monitoring committee) to consider safety and dose modifications with respect to treatment arm. Once the study is suspended, it would only be reopened if modifications could be made, and approved by the DSMC and the UW-IRB, to assure that patient safety is reestablished. If not, the study would be closed.

B. Endpoints

Patients will come off study at the time of radiographic disease progression, with progression being defined only AFTER the first 3-month staging evaluation, at the time of undue toxicity (as defined below), or at the discretion of the patient and treating physician that other therapies for prostate cancer are warranted. Patients should be discouraged from discontinuing protocol treatment for PSA rise only. Patients will continue to have blood drawn for immune studies, as per study calendar, up to one year after screening, even if off study prior to that time. The 6 month visit, in particular, is important to collect for the purpose of endpoint analysis. Subjects who have not come off study earlier for these reasons will come off study at the end of the one-year treatment period.

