The primary endpoint of the trial will be an immunological endpoint – the detection of augmented numbers of PAP-specific effector (IFN γ -secreting and/or granzyme B-secreting) and memory (proliferating) T-cell immune response after immunization, using blood obtained at 6 months for the primary analysis compared with pre-treatment. Immune response will be determined as a static time point at 6 months, and “durable” immune responses will also be determined by evaluation at 3, 9, and 12 months after study entry.

All subjects will undergo radiographic imaging (CT of abdomen and pelvis and bone scan) prior to treatment, and at 3-month intervals (or as clinically indicated). Radiographic disease progression will be defined using both RECIST 1.1 and PCWG2 published criteria [49], as detailed in Section 7. Based on the prior trials leading to the approval of sipuleucel-T, and because immune therapies are expected to require up to several months before radiographic responses or stabilization might be observed, the radiographic studies obtained at 3 months will not be used to define progression, rather will be used as the baseline for future comparison. That is, while baseline studies will be obtained prior to study registration, and radiographic progression may be expected in 50% of patients at 3 months, this will not be used to define progression necessitating patients come off study, rather disease progression occurring after this initial 3-month period. Time to progression will be determined from registration for all subjects. 1-year progression-free survival will be calculated for each treatment arm, as well as the median progression-free survival.

PSA doubling times will be calculated from all available values obtained within 3-6 months from the same clinical laboratory (when feasible) prior to study enrollment, up to and including the baseline value, and used to determine a pre-treatment PSA doubling time. Similarly, a post-treatment doubling time will be calculated from all PSA values obtained beginning with the PSA value at day 1 and continuing until the end-of study (or 1-year) value.

7. Measurement of Effect

A. Malignant Disease Evaluation

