All other lesions or sites of disease that do not meet the criteria for target lesions, including those on bone scintigraphy. Measurements of these lesions are not required, but the presence or absence of each should be noted throughout the study.

a. Complete Response (CR)

The disappearance of all nontarget lesions and undetectable PSA tumor marker levels. To be assigned a status of complete response, changes in tumor measurements must be confirmed by repeat assessments performed **no less than four weeks** after the criteria for response are first met.

b. Incomplete Response/Stable Disease (SD)

The persistence of one or more nontarget lesion(s) and/or the persistence of detectable serum PSA tumor marker levels. To be assigned a status of stable disease, measurements must have met the stable disease criteria at least once after study entry at a minimum interval of 12 weeks.

c. Progressive Disease (PD)

The appearance of one or more new lesion(s) and/or unequivocal progression of existing nontarget lesions.

NOTE: For lesions only detectable by bone scan, the appearance of ≥ 2 new lesions, with symptoms, will constitute disease progression. Without symptoms, and if no other evidence of disease progression (no progressive disease by PSA or measurable disease criteria), progression must be documented with repeat bone scintigraphy at least 6 weeks later demonstrating ≥ 2 new lesions. This is to eliminate the possibility of flair responses seen on bone scans.

3. Symptomatic Deterioration

Patients with a global deterioration of health status requiring discontinuation of treatment without objective evidence of disease progression at that time should be classified as having symptomatic deterioration.

4. PSA Progression

While PSA values will be collected, and PSA kinetics (PSA responses and maximal changes in PSA by waterfall plots) monitored as secondary endpoints, PSA rise will not be used to determine objective disease progression. Similar to the radiographic studies above, PSA progression or response will be defined using both pre-treatment (study entry) and 3-month values as baseline values.

- a. **PSA Complete Response:** Decrease in PSA to <0.2 ng/mL and confirmed with PSA measurement a minimum of four weeks later (confirmed PSA CR). There must be no evidence of radiographic progression.
- b. **PSA Partial Response:** Greater than or equal to 50% reduction in baseline PSA. There must be no evidence of radiographic progression.

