- c. **Best Response:** This is calculated from the sequence of objective statuses. The date of response will be defined as the first date at which PSA declined from baseline or normalized.
 - i. **Confirmed PSA PR:** Two or more objective statuses of PSA PR or better a minimum of four weeks apart documented before progression. Best response for objective disease must be stable/no response or better.
 - ii. **Unconfirmed PSA PR:** One objective status of PSA PR documented before progression, but not qualifying for confirmed PSA PR. Best response for objective disease must be Stable/no response or better.
 - iii. **No PSA Response:** Objective PSA status does not qualify as a PSA PR or unconfirmed PSA PR.
 - iv. **Inadequate Assessment, response unknown:** When best response for objective disease is inadequate or unknown or when PSA has been inadequately assessed, then PSA response will be coded likewise.
- d. **PSA Progression:** Although not considered progression per the primary objective of this study, time to PSA progression will be used for secondary analyses. PSA progression will be defined as a **50%** increase in PSA over the nadir PSA, and ≥ 2 ng/mL above the nadir, confirmed by a second value 3 or more weeks later (i.e. confirmed rising trend). If no on-study reduction has occurred, nadir would be the baseline value (pre-treatment or month 3 time point for analyses).

C. Evaluation of Patient's Best Overall Response

The best overall response is the best response recorded from baseline until disease progression/recurrence, taking as reference for progressive disease the smallest measurements recorded after baseline. The table below provides overall responses for all possible combinations of tumor responses in target and nontarget lesions, with or without new lesions.

To be assigned a status of complete or partial response, changes in tumor measurements must be confirmed by repeat assessments performed **no less than four weeks** after the criteria for response are first met.

To be assigned a status of stable disease, measurements must have met the stable disease criteria at least once after study entry at a minimum interval of 12 weeks.

Overall Response for all Possible Combinations of Tumor Response

Target Lesions	Nontarget Lesions	New Lesions	Overall Response
CR	CR	No	CR
CR	Incomplete response/SD	No	PR
PR	Non-PD	No	PR
SD	Non-PD	No	SD
PD	Any	Yes or No	PD
Any	PD	Yes or No	PD
Any	Any	Yes	PD

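### Radiographic PFS: whether bone-only progression needs confirming depends on PSA, against the plan's own statement, and no scheduled scan can confirm lesions first seen at week 48

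*Combined protocol and SAP*

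**What the plan says.** The NOTE in Section 7.B.2.c treats two or more new bone-scan lesions with symptoms as progression outright. Without symptoms, it adds a condition: "if no other evidence of disease progression (no progressive disease by PSA or measurable disease criteria), progression must be documented with repeat bone scintigraphy", and the repeat must be "at least 6 weeks later demonstrating ≥ 2 new lesions". The reason given is: "This is to eliminate the possibility of flair responses seen on bone scans".

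Section 7.B.4 then states that "PSA rise will not be used to determine objective disease progression". Section 7.B.4.d defines PSA progression for secondary analyses: a 50% rise and at least 2 ng/mL over nadir, confirmed by a second value three or more weeks later, judged against either the pre-treatment or the month-3 baseline. On PSA timing, footnote d of the study calendar says "PSA measurements must be performed at the 3-month intervals defined, but can be more frequent if clinically indicated".

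Bone scans are scheduled before treatment and at months 3, 6, 9 and 12 (Section 9.O puts the last at week 48, plus or minus 7 days). Section 6.B also allows scans when clinically indicated, and says "Subjects who have not come off study earlier for these reasons will come off study at the end of the one-year treatment period". Long-term follow-up (Section 9.P) is annual, by telephone if the patient is not already seen in clinic, and lists no imaging.

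Section 3.B names 12-month radiographic PFS as a secondary objective. Section 12.C.2.2 defines it as the proportion progression-free at the 12-month assessment, and Section 12.G.4.1 estimates it by Kaplan-Meier in each arm.

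**The concern.** The two PSA statements do not fit together. Take two asymptomatic patients with the same two new bone lesions and no measurable-disease progression. The one with PSA progression has an event now. The other has an event only if a later scan confirms it. Their scans are identical, yet event status, or event date, can differ because of PSA.

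The PSA route is also loosely specified. The NOTE does not say which PSA baseline applies, and extra PSA draws are discretionary in an open-label trial.

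The second gap is at the end of the schedule. The assessment that defines 12-month PFS is the one scan with no scheduled successor, and the plan does not say what becomes of bone-only lesions first seen there.

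The same classification feeds the comparison of PFS between arms (Section 12.G.4.2) and the regression of 12-month PFS on immune response (Section 12.G.5.3). Unless it is settled beforehand, it will be settled patient by patient after the scans are known.

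**Working it through.** The plan gives no expected PFS rate, so there is no figure to reproduce. Three checks apply.

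**1. When PSA changes the outcome.** Patients without symptoms or measurable-disease progression, with at least two new bone lesions:

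- PSA progression present: no repeat scan required; event.
- PSA progression absent: event only if a scan at least 6 weeks later shows at least two new lesions.

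PSA is the only input that differs. If the second patient's event were dated at the confirming scan, it would fall at least 6 weeks later, or 36 − 24 = 12 weeks later on scheduled scans. No text says which scan sets the date.

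**2. Which findings have a scheduled confirming scan.** Inputs: scans at weeks 12 (the baseline for progression), 24, 36 and 48; minimum interval 6 weeks.

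| First seen | Earliest confirmation | Scheduled scan that serves |
|---|---|---|
| Week 24 | 24 + 6 = 30 | Week 36 |
| Week 36 | 36 + 6 = 42 | Week 48 |
| Week 48 | 48 + 6 = 54 | None |

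Visit windows do not change this. With plus or minus 7 days, a week-48 scan falls at weeks 47 to 49 and can be confirmed from weeks 53 to 55 after day 1. If the separate 7-day scan window is added, the range is 52 to 56. The shortest week-36 to week-48 gap with both windows is 46 − 38 = 8 weeks, still above 6, so only week 48 is affected. Twelve months is 365.25 / 7 = 52.2 weeks, so the nominal week 54 also falls after the 12-month point. A PSA rise first seen at week 48 likewise has no scheduled second value to confirm it.

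**3. Possible size at week 48 (assumed inputs).** Let progression after the week-12 baseline be exponential with median m weeks: S(t) = exp(−ln 2 × (t − 12) / m). Let q be the share of progressions that are bone-only, asymptomatic and without PSA progression. The share of an arm first detected at week 48 and left uncounted is q × [S(36) − S(48)]. Neither m nor q is in the documents; the ranges used are m = 12 to 36 and q = 5% to 30%.

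| m (weeks) | S(36) | S(48) | New at week 48 | Uncounted, q = 5% | Uncounted, q = 30% |
|---|---|---|---|---|---|
| 12 | 0.250 | 0.125 | 0.125 | 0.6 points | 3.8 points |
| 24 | 0.500 | 0.354 | 0.146 | 0.7 points | 4.4 points |
| 36 | 0.630 | 0.500 | 0.130 | 0.7 points | 3.9 points |

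With 15 patients per arm (Section 12.F), this is 15 × 0.0062 = 0.1 to 15 × 0.0439 = 0.7 patients. A single reclassified patient moves an arm's rate by 1/15 = 6.7 points.

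**The case against.** The strongest reply is that PSA only waives a repeat scan. At least two new bone lesions are always required, and Section 7.C.6.b, which says the marker alone does not assess response, suggests that Section 7.B.4 means PSA by itself. So a reader who infers that PSA decides progression goes too far. The reply stands on that, but the literal conflict remains, and so does the effect on asymptomatic bone-only cases.

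A reader might also infer that a week-48 finding is beyond confirmation. The documents do not support this: clinically indicated scans are allowed. Symptoms, measurable-disease progression or PSA progression already confirmed would also remove the need for a repeat. What holds is that no scheduled scan serves.

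A third tempting inference is that the rule favors Arm 2 because the vaccine slows PSA. The doubling times in Section 2.D (medians 6.5 months before and 8.5 months on treatment) come from stage D0 patients given the DNA vaccine without sipuleucel-T. They are not a contrast between these arms or in this population. With scheduled PSA visits 12 weeks apart after month 3, a modest slowing need not change the visit at which progression is recorded.

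Finally, some unconfirmed lesions may be flare, which the rule exists to exclude, so counting them all as events has its own error. This stands and is why a sensitivity analysis is needed. It is also fair that an analysis rule leaves some PSA dependence: a patient who leaves study after a PSA-waived progression has no later scan, while a PSA-stable patient may have one that does not confirm. First-scan dating removes the difference in dates when lesions are confirmed; it does not remove this residual.

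**Conclusion.** The point holds, with moderate confidence. The NOTE makes confirmation depend on PSA, against Section 7.B.4, and this can alter the status or date of asymptomatic, bone-only events. The plan also provides no scheduled confirming scan after week 48, no dating rule, and no classification for unconfirmed findings at that visit.

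It does not follow that 12-month PFS is certainly overstated. That is the likely direction if unconfirmed findings count as progression-free, which the plan does not say. The size cannot be derived from the documents. The 0.6 to 4.4 points in an arm rest on the assumed exponential model and the assumed ranges for m and q, and amount to less than one patient per arm. The issue merits a change because arms of 15 make the rate sensitive to a single classification. The endpoint is secondary, and the primary immune endpoint is unaffected.

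**What to change.** For the PFS analysis only:

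- **One bone-only rule.** Apply the same rule in both arms without reference to PSA. Date a confirmed event at the first scan showing two or more new lesions.
- **Last-scan handling.** Where such lesions are first seen on the week-48 or last on-study scan and no later scan exists, count them as an event on that date. Add a sensitivity analysis that censors them instead, because some may be flare, and name the censoring date. Censoring on the week-48 date gives nearly the same Kaplan-Meier value as counting the patient progression-free, so the two analyses show the range.

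The protocol team must reconcile the two PSA statements in Section 7.B. When a patient leaves treatment or study is a clinical matter and is left to them.

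The cost is protocol and SAP wording, with no added scans. The small downside is that a few unconfirmed findings will count as events in the main PFS analysis.

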 pTVG-HP (100 μ g) with rhGM-CSF (208 μ g) administered intradermally (i.d.) biweekly 4 times, then every 3 months to complete a 1-year treatment period (i.e. weeks 6 (day 43), 8 (day 57), 10 (day 71), 12 (month 3), then months 6 and 9)

A. **Study Arm Assignment and Toxicity Assessment**

Patients with asymptomatic-to-minimally-symptomatic, castrate-resistant, metastatic prostate cancer, with evidence of progressive disease, and a calculable PSA doubling time with at least 3 serum PSA values collected over a minimum of 3 months, will be invited to participate. These are subjects who would be eligible to receive sipuleucel-T as routine standard of clinical care. Subjects will be randomly assigned to a treatment group, stratified by pre-treatment estimated survival (< 18 months, ≥ 18 months), using the Halabi nomogram [50], and using laboratory/clinical data collected at screening for this determination. This stratification was chosen given the identification in a previous clinical trial that patients with more indolent disease characteristics appeared to have a greater benefit from vaccine treatment in terms of overall

survival, and the specific use of an 18-month cutoff is currently being used in prospective evaluation of other vaccine trials [51]. Given the absence of significant adverse events observed in previous clinical trials with either sipuleucel-T or pTVG-HP, no adverse events > grade 2 are anticipated. However, all study patients will be evaluated for evidence of toxicity, and further accrual to either treatment arm will be discontinued if the toxicity rate is deemed to be excessive. A toxicity rate of 20% for Grade 3 events (or Grade > 1 autoimmune events) or 10% Grade 4 events given an attribution of at least possibly related to study treatment will be considered excessive. Grade 3 limited site reactions (lasting < 48 hours) and fevers/chills (lasting < 48 hours) will be excluded from this assessment as expected possible adverse events of limited duration.

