A treatment-limiting toxicity will be defined as any Grade 3 or greater toxicity (using the NCI Common Terminology Criteria version 4, Appendix C) with an attribution of at least possibly related to the study or treatment procedures, and occurring between the pre-study visit and within one month of the final immunization. For purposes of this study, a Grade 2 autoimmune toxicity will be considered equivalent to a Grade 3 toxicity. If a patient develops Grade 3 toxicity with an attribution of at least possibly related to vaccine, the vaccination schedule will be held until the toxicity resolves to Grade 2 or less (Grade 1 for autoimmune toxicity). There will be no dose reductions due to adverse events. If a patient develops a second Grade 3 event (or Grade 2 autoimmune toxicity) that is believed at least possibly due to treatment, or any Grade 4 event, no further vaccinations will be given and the patient will be removed from study. If the adverse event occurs during the initial 12 weeks of treatment, a treatment delay of up to one week will be permitted, with the expectation that the event resolve to \leq grade 1 for retreatment, and that subsequent immunizations will follow at 2-week intervals. A delay $>$ 1 week will result in a skipped dose. If the adverse event occurs during the 3-month booster phase, vaccination will be held in the event of toxicity attributed to vaccination. If the toxicity observed is believed to be a result of the immune response generated, a regimen of corticosteroids may be administered, as clinically indicated, and after discussion with the study and local PIs. The following dose schedule could be used:

Day 1: Intravenous Solu-Medrol at 1 mg/kg IV q12 hr

Day 2: Intravenous Solu-Medrol at 1 mg/kg IV x 1

Day 3-4: Prednisone at 30 mg p.o. bid

Day 5-6: Prednisone at 15 mg p.o. bid

Day 7-8: Prednisone at 10 mg p.o. bid

Day 9-10: Prednisone at 10 mg p.o. qd

Day 11-12: Prednisone at 5 mg p.o. qd

Mild, low-grade fevers and chills, and local skin site reactions, are expected events following immunization and/or treatment with GM-CSF. Grade 1 events will not be treated with anti-inflammatory agents unless they persist 48 hours after an immunization. Constitutional inflammatory events $>$ grade 1, or persisting beyond 48 hours after immunization, will be managed with ibuprofen, if needed, up to 600 mg three times daily.

9. Plan of Treatment

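### Section 8 gives two recovery grades for resuming DNA vaccination after a non-autoimmune Grade 3 toxicity in the first 12 weeks, and does not say which one prevails

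*Combined protocol and SAP*

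**What the plan says.** All the relevant rules stand in one paragraph of Section 8 (Definition and Management of Limiting Toxicities and Adverse Events).

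- **General hold.** The trigger is: "If a patient develops Grade 3 toxicity with an attribution of at least possibly related to vaccine". The consequence is: "the vaccination schedule will be held until the toxicity resolves to Grade 2 or less (Grade 1 for autoimmune toxicity"). No period is specified.
- **Initial 12 weeks.** "If the adverse event occurs during the initial 12 weeks of treatment, a treatment delay of up to one week will be permitted". The sentence goes on to expect recovery to at most "grade 1 for retreatment, and that subsequent immunizations will follow at 2-week intervals". A longer delay means that the dose is skipped.
- **Booster phase.** "If the adverse event occurs during the 3-month booster phase, vaccination will be held in the event of toxicity attributed to vaccination". This sentence gives no recovery grade.
- **Autoimmune events.** "a Grade 2 autoimmune toxicity will be considered equivalent to a Grade 3 toxicity".
- **Removal.** A patient leaves the study after a second Grade 3 event (or Grade 2 autoimmune toxicity) thought at least possibly due to treatment, or after any Grade 4 event.

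Section 6 schedules the Arm 2 immunizations at "weeks 6 (day 43), 8 (day 57), 10 (day 71), 12 (month 3), then months 6 and 9". Section 9 (Plan of Treatment) sets out the visits and their windows but gives no recovery grade.

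**The concern.** One sentence sets the recovery grade at 2 and another, three sentences later, sets it at 1. Their scopes overlap, because the general sentence is not restricted to any phase, and neither says that it gives way to the other. Two clinicians following the same paragraph could therefore treat the same patient differently.

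The rule decides whether a patient with a continuing vaccine-related Grade 2 event is given the vaccine again. It also decides how many DNA doses that patient has received when the 6-month blood is drawn for the primary endpoint. With 15 patients planned per arm (Section 12.F), handling of individual patients ought to be uniform. Section 16.D permits no deviations except for patient safety, so following either sentence could be recorded as a departure from the other.

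**Working it through.** The documents give no figure to reproduce, because the point concerns wording. The check applies both sentences to each combination of period, event type and grade after recovery.

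| Case | General sentence | Phase sentence | Result |
|---|---|---|---|
| Initial 12 weeks, non-autoimmune, now Grade 2 | Hold ends | Grade 1 or less expected, so not met | **Conflict** |
| Initial 12 weeks, non-autoimmune, now Grade 1 or less | Hold ends | Met | Agree |
| Initial 12 weeks, autoimmune | Grade 1 required | Grade 1 or less expected | Agree |
| Booster phase, either type | Grade 2 or less; Grade 1 if autoimmune | Hold, no grade given | No conflict; the general sentence supplies the grade |

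Only the first row conflicts.

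**Which doses.** The trigger is toxicity at least possibly related to vaccine. Section 9 lists vaccine inoculations separately from sipuleucel-T infusions, so vaccine is taken here to mean pTVG-HP with GM-CSF. Immunization #1 (day 43) cannot then be held for toxicity from a product not yet given. The decisions exposed are those for #2 (day 57), #3 (day 71) and #4 (day 85), so at most three.

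Dose #4 is at the boundary. Day 85 is 84 days, or exactly 12 weeks, after day 1. Section 6 counts #4 among the four biweekly doses, while the study calendar footnote and Section 9 give it the window of the quarterly doses. If #4 is left out, two decisions remain. Dose #5 is due at week 24, roughly 12 weeks after #4, so a one-week allowance has little bearing on it.

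**What differs for the patient.** Suppose the event is at Grade 2 when a dose is due.

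- Under the general sentence the hold has ended.
- Under the 12-week sentence the dose waits for up to one week and is skipped if the event has not improved by then.

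The difference is therefore a delay or a skipped dose.

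**How often.** The documents give no rate for this combination of products. Section 6.A anticipates no events above grade 2. Section 2.D reports 22 patients given this DNA vaccine with GM-CSF. One had a grade 3 amylase judged unrelated to treatment, and there was no other event above grade 2. Taking this as 0 related events in 22, and assuming that the rate carries over:

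- One-sided 95% upper bound: 1 − 0.05^(1/22) = 0.127, or 12.7%.
- Among 15 Arm 2 patients: 15 × 0.127 = 1.9.

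This is a rough ceiling on patients with any related Grade 3 event. Those who are also at exactly Grade 2 when a dose falls due would be fewer. The earlier patients had not received sipuleucel-T first, so the carry-over is an assumption.

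**The case against.** The strongest reply is that the paragraph has a natural structure: a general hold, then one sentence for each phase. On that reading the 12-week sentence adds a stricter condition for its own period and the general sentence covers the rest. The later sentence also speaks of an expectation, which is softer than a requirement. This reading is plausible, but it is not written down. The text does not say that the general Grade 2 threshold is confined to the booster phase. If the expectation is only advisory, nothing says when Grade 2 would be acceptable for retreatment.

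The reply does succeed in limiting the scope. A reader might infer any of the following, and the documents do not support them:

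- **That the rules conflict throughout.** They agree for autoimmune events, and the general sentence supplies a grade in the booster phase.
- **That four of the six doses are exposed.** Four doses are scheduled by day 85, but #1 cannot follow a toxicity from the DNA vaccine.
- **That the patient might be barred from continuing.** The stated result is a delay or a skipped dose. Removal has its own, separate triggers.
- **That the analysis sets change.** Evaluability for the primary endpoint (Section 12.C.2.6) depends on completing sipuleucel-T and having a month-6 assessment, not on DNA doses. The per-protocol definition (Section 12.C.2.7) asks for adequate compliance without a dose count, so any effect on it is speculation.
- **That sites might diverge.** This is a single-institution trial, and Section 16.B provides weekly review of adverse events. The risk is inconsistency between clinicians or between patients.

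**Conclusion.** The contradiction is real and narrow. It concerns Arm 2 patients with a non-autoimmune, vaccine-related Grade 3 toxicity in the initial 12 weeks that has come down to Grade 2 and no further. At most three dosing decisions per patient are exposed, or two if #4 is treated as a quarterly dose. This count rests on reading vaccine as the DNA product.

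Few patients should be affected: the ceiling is about two of 15 if the earlier DNA vaccine experience carries over, and probably fewer. No sample size, power or significance level depends on the point. It still merits correction, because it is a retreatment safety rule that gives two answers, and because the doses concerned are among those scheduled before the 6-month primary assessment.

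**What to change.** The sponsor's clinical team should reconcile the two sentences in Section 8 so that a single recovery criterion applies to non-autoimmune events in the initial 12 weeks. They should also state whether the general sentence governs the booster phase, where the phase-specific sentence gives no grade. Which grade to adopt is a clinical decision on which this review takes no view.

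The cost is a wording change to one paragraph, made by protocol amendment with IRB approval as Section 16.D requires. The statistical design and analyses do not change.
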